4.1.1 Hypothesis	
4.1.2 Sample Size	
4.1.3 Outcome Measures	17
4.1.3.1 Genetic and Metabolic markers	17
4.1.3.2 DR severity level	18

CI	HAPTER 5: REFERENCES	20
	4.1.5 Main Statistical Analyses	18
	4.1.4 Descriptive Statistics	18

Chapter 1: Introduction

2	1.1 Background
3 4 5 6 7 8 9	Diabetic retinopathy (DR) and associated changes are considered a leading cause of blindness in the western world. Long-term diabetes status for ≥10 years leads to DR in up to 80% of affected patients. Different factors, including clinical, genetic, epigenetic, biochemical, and molecular factors, have been shown to contribute to the risk of diabetic complications. Amongst these, a specific class of sphingolipids, the deoxysphingolipids, have been demonstrated to be elevated in both type 1 and 2 diabetes³, and to be associated with an increased risk of developing diabetic polyneuropathy.⁴
10 11 12 13 14 15 16 17 18	Deoxysphingolipids are increased in patients with diabetes mellitus type 2 ^{3 7} as well as in patients with metabolic syndrome. ⁸ In type 1 diabetes, elevated circulating levels of deoxysphingolipids have been shown to be associated with an increased risk of diabetic polyneuropathy. ⁴ Furthermore, a correlation of retinal disease severity and circulating deoxysphingolipid levels has recently been shown in another retinal disease, macular telangiectasia type 2 (MacTel). ⁹ Different factors have been displayed to be associated with the development of diabetic retinopathy, including the duration of diabetes ¹⁰ , HbA1c levels ¹¹ and microalbuminuria. ¹² So far, associations between sphingolipid metabolism and the risk for developing diabetic retinopathy as well as the severity of diabetic retinopathy have not been examined.
20	1.2 Rationale
21 22 23 24 25 26 27	A Randomized Clinical Trial Evaluating Fenofibrate for Prevention of Diabetic Retinopathy Worsening (Protocol AF) is a randomized clinical trial that will evaluate the effect of fenofibrate compared with placebo for prevention of DR worsening through 6 years of follow-up in eyes with mild to moderately severe non-proliferative DR (NPDR) and no CI-DME at baseline. While the primary objective is to determine if fenofibrate is effective at preventing DR worsening, an additional goal is to collect information on potential predictive biomarkers via blood sampling over the course of DR progression.
28 29 30 31 32 33 34 35 36	To help evaluate potential predictive biomarkers across varying levels of DR severity, Protocol AFA will recruit populations with DR severity differing from the Protocol AF cohort. The study visit procedures for participants enrolled in Protocol AFA will mirror those from Protocol AF at the Screening visit, with the exception that ancillary ocular procedures (OCTA and Contrast Sensitivity) typically performed at randomization will also be performed. As detailed in the Statistical Considerations chapter below, data from Protocol AF participants (who consented to allow the sharing of de-identified data and de-identified serum sample use for future research) and also consented to Protocol-GENES will be pooled with the Protocol AFA participants to evaluate changes across the DR severity spectrum.
37 38 39 40 41	Protocol AFA is a collaborative effort between the Jaeb Center for Health Research and the Lowy Medical Research Institute (LMRI), Ltd. LMRI will be performing the metabolite analyses with the de-identified serum samples and also will be submitting a request to the JCHR IRB to obtain samples from the Protocol-GENES for genetic analyses under this protocol for the participants contributing data from the Protocol AF cohort. LMRI will not be saving (banking)

- 42 the genetic samples for future research and will be performing all sample testing at facility(ies)
- within the United States in accordance with the terms of written agreement(s). This protocol
- serves to describe the new cohort being enrolled for AFA as well as describe the planned
- analyses from the cumulative data and samples, as specified, for this initiative.

46 **1.3 Objectives**

47

48

49

50

51

- 1. Determine if circulating metabolites, including sphingolipids, are associated with severity of DR in participants with diabetes mellitus type 2.
- 2. Identify metabolic risk and protective factors that are associated with the development and progression of DR.

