Chapter 2: Study Enrollment and Screening 119 120 2.1 Participant Recruitment and Enrollment 121 A minimum of 400 participants are expected to be included in the analyses. Recruitment and 122 enrollment for the Protocol AFA cohort will run concurrent with Protocol AF at approximately 80 123 clinical centers in the United States and Canada. 124 Participants who enroll in Protocol AF may contribute data to the analyses in accordance with their 125 informed consent(s) from Protocol AF and Protocol GENES. In addition, there may be participants 126 identified as ineligible for Protocol AF during routine-care examinations who may consent to be part of the AFA cohort. 127 128 2.2 Informed Consent 129 Potential eligibility may be assessed as part of a routine-care examination. Before completing any 130 study procedures or collecting any data for the study, written informed consent will be obtained. 131 (1) Participants potentially meeting eligibility for Protocol AF may complete the informed 132 consent forms (ICFs) for Protocols AF and GENES and proceed with screening thereafter. This group may contribute data to the AFA analyses in accordance with their informed 133 134 consent(s) from Protocol AF and Protocol GENES. 135 (2) Participants not meeting the inclusion criteria of Protocol AF, or who cannot commit to a longitudinal study, may take part by being consented using the ICF for the Protocol AFA 136 cohort, which is designed specifically for participants who are not taking part in Protocols 137 138 AF and GENES respectively. 139 (3) Participants without diabetes may take part by being consented using the ICF for the 140 Protocol AFA cohort. These participants should be in generally good health with no history of diabetes. They should have no eye diseases as evidenced by OCT or color fundus 141 142 photography. Unlike the population with a history of diabetes, these participants will not 143 complete the fluorescein angiography procedure. 144 The study protocol will be discussed with the potential study participant by study staff. The potential study participant will be given the Informed Consent Form to read. Potential study 145 146 participants will be encouraged to discuss the study with family members and their personal 147 physicians(s) before deciding whether to participate in the study. 148 As part of the informed consent process, each participant will be asked to provide authorization 149 for release of personal information. The investigator, or his or her designee, will review the study-150 specific information that will be collected and to whom that information will be disclosed. After 151 speaking with the participant, questions will be answered about the details regarding authorization. 152 A participant is considered enrolled when the applicable informed consent forms have been signed.

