4.1.1 Hypothesis

352

355

358359

360

361

362

363

364

365

366

367

368

Null Hypothesis (H₀): There are no significant genetic or metabolic dysregulations associated with the development and progression of diabetic retinopathy.

Alternative Hypothesis (H_1) : There exist some genetic or metabolic that are associated with the development and progression of diabetic retinopathy.

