4.1.3 Outcome Measures

The primary outcome measure will be to measure circulating metabolites and quantify genetic markers (see 4.1.3.1) in patients of different DR severity stages (Group 1-4, Table 1) and in healthy control participants.

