393 394 395 396 397 398 399 400	To evaluate the relationships between genetic and metabolic levels with disease severity, different linear regression analyses will be performed. Depending on the data at hand the tools to perform such analyses will vary but in general these will be multivariable linear regression approaches that adjust for potential imbalances of sample covariates as well as genetic ancestry. Intra-sample correlation will be taken into account by using mixed modelling approaches. The results from these associations will be used in several downstream analyses such as enrichment, burden or over-representation analysis. Post-GWAS analyses such as eQTL, TWAS and Mendelian Randomization will also be performed on these data.
401 402 403 404	Significance Level: A significance level, α , of 0.05 will be used for statistical testing of the study endpoints. False discovery rate due to multiple testing will be addressed by correcting the p-values using the Benjamini-Hochberg adaptive false discovery rate procedure. False discovery rate threshold will be set to 5% to claim significance.
405 406 407 408 409 410 411 412	Multi-omics analysis will be performed by integrating all significant markers found across the genetic and metabolic landscapes. Multivariate co-regulation networks will be constructed to understand potential biological mechanisms underpinning DR. Multivariate clustering techniques will be used to investigate whether combinations of multi-omics factors are able to better stratify across DR severity groups. Prediction models will be built to understand potential diagnostic and prognostic tools. Linear modelling techniques will be implemented to understand potential causative networks across the different 'Omics markers as well as to assess potential interactions across different markers.

- 413 Finally, external data (such as data from UK Biobank or the MacTel consortium studies) will be
- 414 integrated into our study to further expand the discovery potential for this study.

416 Chapter 5: REFERENCES

427

428

429

430

434

435

436

437

438

439

440

441

442

443

444

 [published Online First: 1994/09/01]

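### For metabolites, Objective 2 and the hypothesis claim development and progression of DR, but the protocol defines only a cross-sectional severity outcome

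*Protocol*

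**What the plan says.** Section 1.3 sets two separate objectives. The first is about severity: "Determine if circulating metabolites, including sphingolipids, are associated with severity of DR in participants with diabetes mellitus type 2". The second is about change over time: "Identify metabolic risk and protective factors that are associated with the development and progression of DR". Section 4.1.1 builds the only formal hypothesis on the second idea; its null reads "There are no significant genetic or metabolic dysregulations associated with the development and progression of diabetic retinopathy", and the alternative mirrors it.

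The rest of the protocol describes a severity comparison:

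- **Visits (section 1.2):** "The study visit procedures for participants enrolled in Protocol AFA will mirror those from Protocol AF at the Screening visit", with OCT angiography and contrast sensitivity added. Chapter 3 lists the procedures of one visit and no later one.
- **Consent (section 2.2):** the AFA route is open to people "who cannot commit to a longitudinal study, may take part by being consented using the ICF for the Protocol AFA" cohort.
- **Primary outcome (section 4.1.3):** "The primary outcome measure will be to measure circulating metabolites and quantify genetic markers" across the severity groups and healthy controls.
- **Main analysis (section 4.1.5):** "To evaluate the relationships between genetic and metabolic levels with disease severity, different linear regression analyses will be performed".

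Section 4.1.5 also says "Prediction models will be built to understand potential diagnostic and prognostic tools", without naming a prognostic outcome or a time horizon.

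**The concern.** Development and progression are statements about order in time: the factor is present first, and the disease appears or worsens afterwards. A comparison of metabolite levels between people already at different severity levels carries no such order. A raised metabolite in the proliferative group could have driven the disease, could result from it, or could reflect its treatment.

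Two features of the eligibility criteria add to this. Under section 2.4, Group 1 must have had diabetes for at least 15 years, while Groups 2 to 4 may have had it for any time, so Group 1 is selected for little or no DR despite long exposure. Under section 2.5, earlier DR procedures such as intraocular anti-VEGF or vitrectomy are allowed if they do not hinder grading, so treatment history may differ by severity.

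At stake is what the study may conclude. As written, a significant association between a metabolite and severity would stand as the answer to a hypothesis about progression, and a model fitted to severity groups could be called prognostic.

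**Working it through.** **Step 1: is progression just another word for severity here?** No. Objective 1 already covers severity, so that reading would make Objective 2 redundant for metabolites. The background (section 1.1) also treats the risk of developing DR and the severity of DR as two open questions.

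**Step 2: is a longitudinal DR outcome defined?** The outcome section (4.1.3), the grading section (4.1.3.2) and the analysis section (4.1.5) contain no incident-DR, step-worsening or time-to-event outcome. Mixed models are planned for correlation within a sample, but the only repeated unit in the grading section is the two eyes of one person.

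**Step 3: who could contribute follow-up?** The plan's own totals first:

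- Pool (Table 1): 80 + 200 + 20 + 80 + 20 = 400, as stated.
- AFA cohort (section 1.4): 160 + 20 + 20 = 200, as stated.

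Then follow-up:

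| Set | With possible follow-up | Source |
|---|---|---|
| AFA cohort | 0 of about 200 | one visit only |
| Group 1 (levels 10 to 20) | 0 of 80 | one visit only |
| Whole pool | at most 200 of 400 = 50% | parent trial, 6 years |
| Participants with type 2 diabetes | at most 200 of 380 = 53% | parent trial, 6 years |

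The 380 is 400 less the 20 controls. The 200 is an upper limit, because section 2.3 says most, not all, of Group 2 is randomised in Protocol AF.

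**Step 4: what could that follow-up inform?** Group 2 starts at levels 35 to 47, so DR is already present and only progression could be studied. Group 1 is the only diabetic group that includes people without DR, and it has no later visit. First development of DR therefore cannot be studied longitudinally for metabolites in this pool.

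**Step 5: would a progression analysis in Protocol AF participants be informative? Illustration only.** The protocol gives no worsening rate. Assume that 20 to 30% of 200 worsen, which is 40 to 60 events. With 80% power, the detectable hazard ratio per SD is exp((z for alpha + 0.84)/√events):

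- Nominal two-sided 0.05: exp(2.80/√40) = 1.56; exp(2.80/√60) = 1.44.
- Threshold 0.0005 (assuming 100 metabolites and a conservative 0.05/100): exp((3.48 + 0.84)/√40) = 1.98; exp((3.48 + 0.84)/√60) = 1.75.

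The plan works at a 5% false discovery rate, so the nominal figures are optimistic. The finding does not depend on either pair.

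**The case against.** The strongest reply is that the plan is wider than a severity contrast. Sections 4.1.3.1 and 4.1.5 include SNP typing, polygenic scores, Mendelian randomization, prediction models and external data. The hypothesis covers genetic as well as metabolic factors. Germline variants precede DR, so disease and treatment cannot have caused them, although selection could still bias the comparison. A Group 1 with long diabetes and little or no DR also bears on development for those variants. All of this stands, and it confines the point to metabolites. It does not remove the point, because none of these analyses is tied to a longitudinal DR outcome and Objective 2 is expressly about metabolic factors.

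A second reply is that parent-trial follow-up may yet be used. Section 1.2 mentions blood sampling in Protocol AF over the course of progression and planned analyses of cumulative data, and Chapter 4 defers detail to an SAP. This also stands in part: silence is not exclusion. But an SAP cannot create follow-up for the AFA cohort, and the objective and hypothesis sit in the protocol.

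A third reply is that this is a minimal-risk ancillary study in which the outcome, the pooling and the main regressions consistently speak of severity. That is so, and it makes Objective 2 and the hypothesis the parts out of line.

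**Conclusion.** The point holds for metabolic factors. The protocol states a longitudinal objective and hypothesis but defines only a cross-sectional outcome and severity-based main models. For development, the gap cannot be closed within this pool: 0 of 80 in Group 1 have a planned later visit, and the Protocol AF participants already have DR. For progression it could be closed in at most half the pool, but the protocol names neither the outcome nor the handling of randomised fenofibrate.

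A reader might go further and infer that every planned analysis is a single-visit severity comparison, that the whole hypothesis is untestable, or that parent-trial follow-up will not be used. The document does not support these readings: it plans genetic and external-data work, its hypothesis is partly genetic, and it does not rule out follow-up data.

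The conclusion rests on the text and the group targets alone. The hazard ratios above rest on an assumed worsening rate and should not be cited as a property of the plan.

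**What to change.** 1. Reword Objective 2 (section 1.3) and the metabolic part of both hypotheses (section 4.1.1) as association with DR severity at a single visit. If that leaves Objective 2 the same as Objective 1, merge them.
2. In section 4.1.5, describe metabolite prediction models built on severity groups as diagnostic, not prognostic.
3. Leave the genetic aims, including polygenic scores and Mendelian randomization, as they are.
4. If a progression aim for metabolites is to be kept, define a DR-worsening outcome in the pooled Protocol AF participants. Relate the pre-treatment metabolite level to worsening, adjust for randomised arm and baseline severity, and apply the 5% false discovery rate. Limit metabolite progression claims to that analysis. Development must still be dropped for metabolites.

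Items 1 and 2 are a wording amendment to three sections, with no new visits or samples. Item 4 adds one analysis of parent-trial data, available only once those outcomes are released and with precision that depends on an event count the protocol does not give. The downside is a narrower headline claim.

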1.4 Protocol Synopsis

- 52 Protocol AFA will enroll approximately 200 participants whose data will be pooled with
- 53 approximately 200 randomized Protocol AF participants to compare metabolic changes
- associated with DR severity level. To conduct the analyses, participants from Protocols AF and
- AFA with diabetes will be placed into Groups 1 through 4, based on level of DR severity, as seen
- in Table 1. The new AFA cohort will consist of approximately 160 participants with diabetes
- 57 mellitus type 2 and DR severity levels falling under the AF eligibility cut-off (No DR to Mild,
- Group 1) or above the cut-off, Group 4 (PDR, Group 4), with 20 additional participants having
- 59 Severe NPDR (Group 3) as well as 20 participants without diabetes as part of a non-diabetic
- 60 control group (Group 5).
- If both eyes are not of the same DR severity, the participant's worse eye will be decisive for the
- 62 final classification into each of the designated groups. Since classification is based on Reading
- 63 Center assessment of DR severity level, it is possible for cohorts to be overenrolled.
- Additionally, some AFA-enrolled participants may fall in Group 2 and will be included in the
- analysis if AF-only cohort target goal is not otherwise met. Eyes enrolled into Group 3 will be
- based on reading center grading only, consisting of AF screen fail patients and those AFA-
- enrolled eyes intended for other cohorts.

Table 1. Description of Groups for Analyses from Protocols AF & AFA			
Analysis Group Number	Group Description Participants with Type 2 Diabetes, and worse eye :	Target Number of Participants	
AFA Group 1	Absent of DR, or microaneurysms only (Diabetes ≥15 yrs) (DR severity level 10 to 20)	80	
Protocol AF Cohort, Group 2	Mild to moderately severe DR (DR severity level 35 to 47)	200	
AFA Group 3	Severe non-proliferative DR (DR severity level 53)	20	
AFA Group 4	Proliferative DR (DR severity level 61 to 81)	80	
AFA Group 5	Absent of any diagnosis of diabetes and absent evidence of retinal disease as determined by color fundus photography and OCT imaging	20	
Tot	tal Number of Participants in the Analysis Pool (AF & AFA)	400	

68 69 70 71 72	Prior to completing any procedures or collecting any data for this research, informed consent for either Protocols AF and GENES, or Protocol AFA will be obtained (see section 2.2). Participants who screen fail for participation in Protocol AF may still be eligible for Protocol AFA, with rescreening only necessary if sample collection and/or any testing procedures listed below was not completed.
73 74 75 76 77 78 79 80 81 82 83 84	Participants will undergo a screening evaluation to determine eligibility for the AFA cohort. Qualified participants must meet all eligibility criteria. All procedures conducted during the Protocol AF screening visit will likewise be conducted for Protocol AFA participants, including: medical history, visual acuity, OCT, fundus photography, fluorescein angiography (FA), physical exam, fasting blood samples, and urine sample. Non-diabetic patients (Group 5) will not undergo fluorescein angiography. Participants from the Protocol AF cohort must also have provided a genetics sample under DRCR Protocol-GENES to be included in the analyses for Protocol AFA. The study team will follow the DRCR Genetics Project Sample Requests Policy, including the submission of a Secondary Research of Stored Biospecimens xForm, under Protocol-GENES, to the IRB for review and approval. Once approved, the genetic samples from Protocol-GENES can be provided to LMRI to conduct SNP typing on all participants using aliquot(s) from the provided genetics sample.
85	1.5 Potential Risks and Benefits of the Study
85 86	1.5 Potential Risks and Benefits of the Study1.5.1 Known Potential Risks Related to Common Procedures
	·

1.5.2 Risks Related to Confidentiality

do all other procedures.

102

The risk of disclosure of protected health information is very small. Efforts are taken to assure that this does not occur, in compliance with HIPAA.

106	1.5.3 Known Potential Benefits
107 108 109	There will be no direct benefit to the participant from participating in this study. The participant's involvement may further knowledge about the relationship between metabolic levels and DR.
110	1.6 Risk Assessment
111 112	The protocol risk assessment for this non-intervention ancillary study has been categorized as no greater than minimal risk.
113	1.7 General Considerations
114 115 116	The study is being conducted in compliance with the policies described in the study policies document, with the ethical principles that have their origin in the Declaration of Helsinki, with the protocol described herein, and with the standards of Good Clinical Practice (GCP).
117 118	When feasible, data will be directly collected in electronic case report forms, which will be considered the source data.

Chapter 2: Study Enrollment and Screening 119 120 2.1 Participant Recruitment and Enrollment 121 A minimum of 400 participants are expected to be included in the analyses. Recruitment and 122 enrollment for the Protocol AFA cohort will run concurrent with Protocol AF at approximately 80 123 clinical centers in the United States and Canada. 124 Participants who enroll in Protocol AF may contribute data to the analyses in accordance with their 125 informed consent(s) from Protocol AF and Protocol GENES. In addition, there may be participants 126 identified as ineligible for Protocol AF during routine-care examinations who may consent to be part of the AFA cohort. 127 128 2.2 Informed Consent 129 Potential eligibility may be assessed as part of a routine-care examination. Before completing any 130 study procedures or collecting any data for the study, written informed consent will be obtained. 131 (1) Participants potentially meeting eligibility for Protocol AF may complete the informed 132 consent forms (ICFs) for Protocols AF and GENES and proceed with screening thereafter. This group may contribute data to the AFA analyses in accordance with their informed 133 134 consent(s) from Protocol AF and Protocol GENES. 135 (2) Participants not meeting the inclusion criteria of Protocol AF, or who cannot commit to a longitudinal study, may take part by being consented using the ICF for the Protocol AFA 136 cohort, which is designed specifically for participants who are not taking part in Protocols 137 138 AF and GENES respectively. 139 (3) Participants without diabetes may take part by being consented using the ICF for the 140 Protocol AFA cohort. These participants should be in generally good health with no history of diabetes. They should have no eye diseases as evidenced by OCT or color fundus 141 142 photography. Unlike the population with a history of diabetes, these participants will not 143 complete the fluorescein angiography procedure. 144 The study protocol will be discussed with the potential study participant by study staff. The potential study participant will be given the Informed Consent Form to read. Potential study 145 146 participants will be encouraged to discuss the study with family members and their personal 147 physicians(s) before deciding whether to participate in the study. 148 As part of the informed consent process, each participant will be asked to provide authorization 149 for release of personal information. The investigator, or his or her designee, will review the study-150 specific information that will be collected and to whom that information will be disclosed. After 151 speaking with the participant, questions will be answered about the details regarding authorization. 152 A participant is considered enrolled when the applicable informed consent forms have been signed.

2.3 AFA Population Approximately 200 AFA participants will be recruited from clinical centers already certified to

- recruit for Protocols AF and GENES. Data from approximately 200 randomized Protocol AF
- participants that have also consented for Protocol-GENES will be pooled with the AFA-only
- 157 cohort for the analyses.
- Participants diagnosed with diabetes mellitus type 2 will fall into Groups 1, 2, 3, or 4:
- Group 1 DR Severity level 10 to 20 (n=80): participants in Group 1 must have been diagnosed with DM for 15 years or longer.
- Group 2 DR Severity 35-47 (n=200, most of which will be randomized in Protocol AF)
- Group 3 DR Severity level 53 (n=20): participants in Group 3 will qualify based on reading center grading only from eyes enrolled in the other groups.
- Group 4 DR severity level 61 to 81 (n=80)
- 165 The participant's worse eye based on reading center grading will be decisive for the final
- 166 classification of a patient in the above-mentioned categories. Participants in these groups may
- include a participant that screen failed for Protocol AF due to DR severity level or may include a
- participant that was known to be ineligible for Protocol AF and specifically consented as part of
- the AFA-only cohort. Given the rapid rate of progression in level 53 eyes and difficulty in
- capturing key severe NPDR features on imaging, eyes enrolled into Group 3 will be based on
- 171 reading center grading only, consisting of AF screen fail patients and those AFA-enrolled eyes
- intended for other cohorts. Approximately 20 eyes are expected to be included in this group.
- 173 20 participants of generally good health, without any diabetes-related conditions and without any
- evidence of retinal diseases will be enrolled into Group 5 as part of a small non-diabetic control
- 175 group (AFA only cohort). These participants will complete all AFA procedures, with the
- exception of the digital fluorescein angiography.

